6.3.5 Laboratory safety assessment

Blood and urine samples for determination of clinical chemistry, hematology, and urinalysis will be collected at the times indicated in [Table 1](#).

The safety laboratory variables are presented in [Table 3](#).

Table 3 Safety laboratory variables

Clinical chemistry	Hematology
Serum (S)/Plasma (P)-alkaline phosphatase (ALP)	Blood (B)-hemoglobin
S/P-aspartate aminotransferase (AST)	B-hematocrit
S/P-alanine aminotransferase (ALT)	B-absolute leukocyte differential count
S/P-total bilirubin	B-platelet count
S/P-uric acid	Erythrocytes (red blood cell count)
P-glucose	
S/P-albumin	
S/P-calcium, total	
S/P-creatinine	Urinalysis
S/P-potassium	Urine (U)-glucose
S/P-sodium	U-hemoglobin
Total protein	U-protein
Blood urea nitrogen	
Gamma-glutamyl transferase (GGT)	

Proteinuria and hematuria will be measured with a urine dipstick.

All subjects will be tested for HBsAg, HCV antibodies, and HIV at screening.

Urine will be tested for drugs of abuse at screening and at admission to Visits 2, 3, and 4. Drugs of abuse include amphetamines, barbiturates, tricyclic anti-depressants, cocaine, methadone, phencyclidine, tetrahydrocannabinol, and opiates. If a subject tests positive to any of these screening tests, he will be excluded from the study.

An alcohol breath test will be performed at screening and at admission to Visits 2, 3, and 4. Laboratory values outside the reference limit suspected to be of any clinical significance will be repeated. Subjects in whom suspected clinical significance is confirmed, will either not be included in the study or if already enrolled, will be monitored until normalization or for as long as the Investigator considers necessary. Additional laboratory variables may be performed for safety reasons if judged necessary by the Investigator.

Samples will be collected in tubes according to standard routines. The safety laboratory samples will be analyzed using routine methods at the Physicians Reference Laboratory.

For blood volume see Section 7.1.

6.3.6 Physical examination

A full physical examination will be performed by medically qualified individuals at screening and at follow-up. A targeted physical examination will be performed on Day -1 and before discharge on Day 3 of Visits 2, 3, and 4 and will include: general, cardiovascular system, chest, abdomen, and skin. Results will be recorded as an overall normal or abnormal interpretation with a listing of abnormalities.

6.3.7 ECG

A 12-lead paper ECG for safety review by the Investigator will be performed after 10 minutes in the supine position and the outcome of the overall evaluation is to be recorded as normal/abnormal in the eCRF, with any abnormalities specified. The print-out of the ECG is to be signed, dated, and filed in the Investigator's Study File. The ECG measurements will be performed at the time points presented in [Table 1](#).

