2.2 Secondary objective

- To assess the safety and tolerability of co-administration of ticagrelor and cyclosporine in healthy male subjects by assessment of AEs, safety laboratory variables, physical examination, electrocardiogram (ECG), and vital signs

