4.2 Exclusion criteria

Subjects should not enter the study if any of the following exclusion criteria are fulfilled:

1. History of any clinically significant disease or disorder which, in the opinion of the Investigator, may either put the subject at risk because of participation in the study, or influence the results or the subject's ability to participate in the study
2. History or presence of gastrointestinal, hepatic or renal disease, or any other condition known to interfere with absorption, distribution, metabolism, or excretion of drugs
3. Any clinically significant illness, medical/surgical procedure, or trauma within 4 weeks of the first administration of the investigational product
4. A history of hemophilia, von Willebrand's disease, lupus anti-coagulant, or other diseases/syndromes that can either alter or increase the propensity for bleeding
5. A personal history of vascular abnormalities including aneurysms; a personal history of severe hemorrhage, hematemesis, melena, hemoptysis, severe epistaxis, severe thrombocytopenia, intracranial hemorrhage, or rectal bleeding within 1 year (or as judged by the Investigator) prior to Visit 1 or a history suggestive of peptic ulcer disease
6. History of a clinically significant non-traumatic bleed or clinically significant enhanced bleeding risk, as judged by the Investigator

7. History of a previous or ongoing psychiatric disease/condition, including psychosis, affective disorder, suicidality, anxiety disorder, borderline state, or personality disorder
8. Any clinically significant abnormal clinical chemistry, hematology, or urinalysis results as judged by the Investigator
9. Any positive result on screening for serum hepatitis B surface antigen (HBsAg), hepatitis C virus (HCV) antibody, and human immunodeficiency virus (HIV)
10. Abnormal vital signs, after 10 minutes supine rest at screening (may repeat), defined as any of the following:
 - Systolic blood pressure (SBP) >140 mmHg
 - Diastolic blood pressure (DBP) >90 mmHg
 - Pulse rate <40 or >100 bpm
11. Any clinically important abnormalities in rhythm, conduction, or morphology of resting ECG, as judged by the Investigator
12. Prolonged QTcF >450 ms or shortened QTcF <340 ms or family history of long QT syndrome
13. Known or suspected history of drug abuse, as judged by the Investigator
14. Smoking more than 7 cigarettes per week or consumption of more than 3 portions of snuff or the equivalent per week

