12.2.3 Safety and tolerability

All safety data will be listed in subject listings. Continuous variables (hematology, clinical chemistry, and vital signs) will be summarized using descriptive statistics (n, mean, SD, minimum, median, and maximum) by treatment and/or each scheduled assessment point, both as absolute values and as change from baseline. Categorical variables (urinalysis, ECG interpretation) will be summarized in frequency tables (frequency and proportion) by scheduled assessment point. Laboratory values and vital signs outside reference limits will be marked high (H) and low (L) where appropriate.

For laboratory data and vital signs assessments all repeat values will be included in the data listings. For calculation of descriptive statistics the following rules will be applied: for measurement time points before the first dose the last valid repeat value will be used; for measurement time points after the first dose the first valid value will be used; retake of a pre-dose value will not be used if taken after dose. Laboratory values below the detectable limit ($< X$) will be replaced by X when summarizing mean, SD etc.

Abnormalities found in physical examinations will be listed.

Adverse events will be summarized by Preferred Term and System Organ Class using the MedDRA.

The number of subjects who had any AEs, SAEs, discontinuation due to AEs (DAEs), OAEs, AEs with severe intensity, and AEs judged causally related to the investigational product by the Investigator will be summarized. Any SAEs and DAEs will be listed separately.

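### ECG intervals are not collected as data, so a PR, QRS or QTcF change that stays within normal limits would reach no planned eCRF field or table

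*Protocol*

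**What the plan says.** Section 2.2 lists the ECG among the assessments of the safety of co-administration ("physical examination, electrocardiogram (ECG), and vital signs"). Table 1 schedules a 12-lead paper ECG at screening, on Day -1 and Day 3 of each of the three treatment visits, and at follow-up.

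Section 6.3.7 states that "the outcome of the overall evaluation is to be recorded as normal/abnormal in the eCRF"; the same sentence goes on to require that abnormalities be specified. The trace stays on paper: "The print-out of the ECG is to be signed, dated, and filed in the Investigator's Study File". No interval is named as a data item.

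Section 12.2.3 then states: "Categorical variables (urinalysis, ECG interpretation) will be summarized in frequency tables (frequency and proportion) by scheduled assessment point". Treatment is not mentioned for these tables. Numeric summaries are planned for other variables: "Continuous variables (hematology, clinical chemistry, and vital signs) will be summarized using descriptive statistics", in absolute terms and as changes from baseline. Section 11.1 defines a baseline for laboratory tests and for vital signs, but none for the ECG.

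Two further places matter. Exclusion criterion 12 in 4.2 is set in milliseconds ("Prolonged QTcF >450 ms or shortened QTcF <340 ms"), so QTcF has to be read at least for eligibility. Section 6.3.3 makes a worsening ECG an adverse event only if it meets a seriousness criterion or is why treatment was stopped.

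**The concern.** The design is a within-subject crossover with an ECG before and after dosing in every period, so it could support a paired numeric comparison of the combination with each drug alone. The plan reduces each ECG to one overall reading, with a description when something is abnormal. Subjects are healthy men already screened on QTcF, so a systematic interval change of moderate size would seldom alter that reading. The ECG table could look the same whether or not such a change occurred.

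The stake is limited to the ECG part of the secondary objective. The primary pharmacokinetic objectives are untouched.

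**Working it through.** The protocol states no figure on this point, so there is none to reproduce. The finding rests on the text; the arithmetic only shows scale.

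**1. Following a within-limits change through the plan.** Suppose QTcF goes from 400 to 410 ms after dosing.
- 6.3.7: the call stays normal and there is no abnormality to describe.
- 12.2.3: the frequency table is unchanged.
- 6.3.3: it is not an adverse event unless serious or a cause of discontinuation. That section limits such reporting because laboratory tests and vital signs will be summarized in the study report. It applies the limit to the ECG too, whose values are not in that summary.
- What remains is the filed print-out.

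Section 6.1 ties eCRF content to the protocol. A SAP could split the ECG table by treatment, but it could not summarize intervals that were never entered.

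**2. How rarely a shift would cross the upper limit.** Assumptions, none from the documents: QTcF normally distributed, mean 390 to 410 ms, between-subject SD 15 to 20 ms, and a reading called abnormal when QTcF exceeds 450 ms. With P = 1 − Φ((450 − mean − shift)/SD), the extra expected count among 18 completers for a 10 ms shift is:
- Mean 390, SD 15: 18 × (0.0004 − 0.0000) ≈ 0.01
- Mean 400, SD 20: 18 × (0.0228 − 0.0062) = 0.30
- Mean 410, SD 20: 18 × (0.0668 − 0.0228) ≈ 0.8

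**3. What a clean table would bound.** With 0 of 18 abnormal, the one-sided 95% upper limit for the true rate is 1 − 0.05^(1/18) = 15.3%. This is true of any binary outcome at this sample size.

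**4. What recorded intervals would give.** Assume an SD of the within-period change of 8 to 15 ms, independent between periods. The 90% CI half-width for the A minus C difference in change is t(0.95, 17 df) × SD × √2/√18 = 1.740 × SD/3 = 0.58 × SD:
- SD 8 ms: 4.6 ms
- SD 10 ms: 5.8 ms
- SD 12 ms: 7.0 ms
- SD 15 ms: 8.7 ms

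**5. How much drug is left at the Day 3 ECG.** Section 3.2 gives an accumulation ratio of about 1.8 at twice-daily dosing. Assuming simple first-order accumulation over 12 hours, 1.8 = 1/(1 − e^(−12k)), so e^(−12k) = 1 − 1/1.8 = 0.444, k = 0.0676 per hour and the half-life is 0.693/0.0676 = 10.3 hours. The fraction left at 48 hours is 0.444^4 = 3.9%. With a half-life of 20 hours it would be 2^(−48/20) = 19%.

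**6. Workload.** ECGs per subject: 1 + 3 × 2 + 1 = 8. Four intervals give 4 × 8 = 32 entries; adding ECG heart rate gives 5 × 8 = 40.

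**The case against.** The strongest reply is that nothing here is misstated. Section 6.3.7 presents the ECG as a safety review by the investigator, 12.2.3 tabulates the result of that review, and no interval analysis is promised. Physical examination is recorded in the same way. Reading QTcF for eligibility does not make it an outcome, and a categorical call needs no change-from-baseline definition. This stands: the point is a loss of information, not a contradiction.

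Four stronger readings are tempting, and the protocol does not support them.
- A reader might infer that the eCRF receives a bare normal/abnormal flag. It does not: abnormalities must be specified, so an interval judged abnormal would be described.
- A reader might infer that a heart-rate change would go unseen. Pulse rate is a vital sign under 6.3.8, has a baseline in 11.1, and is summarized numerically under 12.2.3.
- A reader might infer that every subject enters with a normal ECG. Criterion 11 excludes only clinically important abnormalities in the investigator's judgement, and no PR or QRS limit is set.
- A reader might infer that the interval data are lost. The print-outs are filed and could be re-read, although nothing in the protocol plans this.

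The objection with most force is about timing. The only in-period post-dose ECG is on Day 3, at about 48 hours, when little ticagrelor remains. A reassuring table of interval changes at that point could mislead as easily as a clean normal/abnormal table. This also stands, and it limits what the fix can deliver.

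**Conclusion.** The point holds as an inexpensive improvement of modest weight. As written, a PR, QRS or QTcF change within normal limits reaches no eCRF field or table and, unless serious or a cause of discontinuation, is not an adverse event. Because the protocol fixes what is recorded, later analysis planning alone cannot repair this. The absence of treatment from the ECG table further weakens the comparison that the objective needs.

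The size is illustrative. Every QTcF figure rests on assumed means and SDs, and the crossing counts also equate an abnormal call with QTcF above 450 ms, a rule that 6.3.7 does not state. Half-widths of 4.6 to 8.7 ms would describe effects at about 48 hours only. A reader might infer that recording intervals would let the study rule out an ECG effect of the combination; with about 4% of ticagrelor left (19% under the longer half-life), it would not do so for the time near peak exposure.

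**What to change.** - **6.3.7:** enter PR, QRS, QT and QTcF from each scheduled ECG in the eCRF, next to the normal/abnormal call and the description of abnormalities.
- **11.1:** define the ECG baseline as Day -1 of the same period.
- **12.2.3:** add the intervals to the continuous variables, summarized by treatment as absolute values and changes from baseline. Tabulate the normal/abnormal call by treatment too, and count values outside the protocol's own 340 and 450 ms limits.
- **Interpretation:** state with these summaries that they describe late effects, at about 48 hours, and do not exclude an effect near peak exposure.

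The cost is about 32 to 40 eCRF entries per subject and one more table. No extra ECG or visit is needed, and no extra reader if the print-outs carry the intervals, which is assumed here.

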6.3.8 Vital signs

Blood pressure and pulse rate will be measured using non-invasive equipment after 10 minutes supine rest on a bed. The vital signs measurements will be performed at the time points presented in [Table 1](#) (pre-dose on Day 1 of Visits 2, 3, and 4).

6.4 Pharmacokinetics

6.4.1 Collection of samples

Blood samples (2 mL) for determination of ticagrelor and its active metabolite (AR-C124910XX) in plasma will be collected at times presented in the study plan table ([Table 1](#)).

Blood samples (1mL) for determination of cyclosporine in blood will be collected at times presented in the study plan table ([Table 1](#)).

Samples will be collected, labeled, stored, and shipped as detailed in the Laboratory Manual.

For blood volume see Section [7.1](#).

6.4.2 Determination of drug concentration

Samples for determination of ticagrelor and its metabolite concentrations in plasma will be analyzed by _____ on behalf of AstraZeneca, using appropriate bioanalytical methods which will be detailed in the Bioanalytical Report appended to the CSR. The lower limits of quantification (LLOQ) of ticagrelor and its metabolite AR-C124910XX in plasma are 1 ng/mL and 2.5 ng/mL, respectively.

Samples for determination of cyclosporine drug concentrations in blood will be analyzed by _____ on behalf of AstraZeneca, using appropriate bioanalytical methods which will be detailed in the Bioanalytical Report appended to the CSR.

6.5 Collection of biomarker samples

Study participants not on any concomitant medications will be offered the option to participate in the biomarker research. After giving written consent for the optional biomarker research, a plasma sample will be collected in accordance with the inclusion criteria and study schedule.

The plasma sample must be collected before administration of any investigational product, according to the study schedule. Only 1 sample should be collected per subject for biomarker research during the study. A 10 mL plasma sample will be collected in a lithium-heparin tube. Samples will be collected, labeled, stored, and shipped as detailed in the Safety Biomarker Laboratory Manual.

Some of the dataset (eg, age, gender, race, body, weight, height, BMI, and fasting state) from the main study may be duplicated within AstraZeneca for exploratory analyses in combination with the optional biomarker data. This information will be provided to AstraZeneca with the biomarker sample shipment. Neither the subject's name nor any other personal identifiers will be part of this dataset. Optional biomarker data will not be reported in the CSR.

For blood volume see Section 7.1.

7. BIOLOGICAL SAMPLING PROCEDURES

7.1 Volume of blood

The approximate total volume of blood that will be collected from each subject in this study is presented in Table 4.

Table 4 Volume of blood to be drawn from each subject

Assessment		Sample volume (mL)	No. of samples	Total volume (mL)
Safety	Clinical chemistry	8.5	8	68
	Hematology	4	8	32
	Serology	8.5	1	8.5
Pharmacokinetic	Ticagrelor and AR-C124910XX	2	26 (13 x 2)	52
	Cyclosporine	1	26 (13 x 2)	26
	Indwelling catheter ^a	2	26	52
Biomarkers (optional)		10	1	10
Total				248.5

a If an indwelling catheter is used, 2 mL of blood will be removed prior to the pharmacokinetic sample collections.

The number of samples collected and the volume required for each analysis may be changed during the study (ie, if additional samples are collected for repeated safety assessments). However, the maximum volume to be collected from each subject will not exceed 450 mL, the same volume as would be collected during a regular blood donation.

7.2 Handling, storage, and destruction of biological samples

The samples will be used up or disposed of after analyses or retained for further use as described below.

7.2.1 Safety samples

Blood samples for safety assessments will be disposed of after analysis.

7.2.2 Pharmacokinetic samples

Samples will be disposed of upon instruction from AstraZeneca, after the CSR has been finalized.

7.2.3 Biomarker samples

Biological samples for biomarker research can be retained on behalf of AstraZeneca for a maximum of 15 years following the last subject's last visit in the study. The results from future analyses will not be reported in the CSR, but separately in a Scientific Report.

7.3 Labeling and shipment of biohazard samples

The Investigator ensures that samples are labeled and shipped in accordance with the Laboratory Manual and the Biological Substance, Category B Regulations (materials containing or suspected to contain infectious substances that do not meet Category A criteria), see [Appendix C](#) International Air Transport Association (IATA) 6.2 Guidance Document.

Any samples identified as Infectious Category A materials are not shipped and no further samples will be taken from the subject unless agreed with AstraZeneca and appropriate labeling, shipment, and containment provisions are approved.

7.4 Chain of custody of biological samples

A full chain of custody is maintained for all samples throughout their life cycle.

The Investigator keeps full traceability of collected biological samples from the subjects while in storage at the study center until shipment or disposal (where appropriate) and keeps documentation of receipt of arrival.

The sample receiver keeps full traceability of the samples while in storage and during use until used or disposed of or until further shipment and keeps documentation of receipt of arrival.

AstraZeneca keeps oversight of the entire life cycle through internal procedures, monitoring of the study center, and auditing of external laboratory providers.

Samples retained for further use are registered in the AstraZeneca biobank system during the entire life cycle.

7.5 Withdrawal of informed consent for donated biological samples

If a subject withdraws consent to the use of donated biological samples, the samples will be disposed of or destroyed, and the action documented. If samples are already analyzed, AstraZeneca is not obliged to destroy the results of this research.

As collection of the biomarker sample is an optional part of the study, the subject may continue in the study even if consent is withdrawn for collection of this sample.

The Investigator:

- Ensures subjects' withdrawal of informed consent to the use of donated samples is notified immediately to AstraZeneca
- Ensures that biological samples from that subject, if stored at the study center, are immediately identified, disposed of or destroyed, and the action documented
- Ensures the laboratory(ies) holding the samples is/are informed about the withdrawn consent immediately and that samples are disposed of or destroyed, the action documented, and the signed document returned to the study center
- Ensures that the subject and AstraZeneca are informed about the sample disposal

AstraZeneca ensures the laboratory(ies) holding the samples is/are informed about the withdrawn consent immediately and that samples are disposed of or destroyed and the action documented and returned to the study center.

8. ETHICAL AND REGULATORY REQUIREMENTS

8.1 Ethical conduct of the study

The study will be performed in accordance with ethical principles that have their origin in the Declaration of Helsinki and are consistent with International Conference on Harmonization (ICH)/Good Clinical Practice (GCP), applicable regulatory requirements and the AstraZeneca policy on Bioethics and Human Biological Samples.

8.2 Subject data protection

The Informed Consent Form will incorporate (or, in some cases, be accompanied by a separate document incorporating) wording that complies with relevant data protection and privacy legislation.

8.3 Ethics and regulatory review

An Institutional Review Board (IRB) should approve the final CSP, including the final version of the Informed Consent Form and any other written information and/or materials to be provided to the subjects. The Investigator will ensure the distribution of these documents to the applicable IRB, and to the study center personnel.

The opinion of the IRB should be given in writing. The Investigator should submit the written approval to AstraZeneca before enrollment of any subject into the study.

The IRB should approve all advertising used to recruit subjects for the study.

AstraZeneca should approve any modifications to the Informed Consent Form that are needed to meet local requirements.

If required by local regulations, the CSP should be re-approved by the IRB annually.

Before enrollment of any subject into the study, the final CSP, including the final version of the Informed Consent Form, is approved by the national regulatory authority or a notification to the national regulatory authority is done, according to local regulations.

AstraZeneca will handle the distribution of any of these documents to the national regulatory authorities.

AstraZeneca will provide regulatory authorities, the IRB, and the Investigator with safety updates/reports according to local requirements, including suspected unexpected serious adverse reactions (SUSARs), where relevant.

The Investigator is responsible for providing the IRB with reports of any serious and unexpected adverse drug reactions from any other study conducted with the investigational product. AstraZeneca will provide this information to the Investigator so that he/she can meet these reporting requirements.

